## 3. DATA MONITORING COMMITTEE REVIEW

An independent data monitoring committee (IDMC) will be established to monitor severe LRTI. The presence of severe LRTI will be determined by the Clinical Endpoint Committee (CEC), a separate committee (see CTP Section 11.9.2). The outcome of the adjudication of the CEC as well as the determination of RSV positivity will be provided to the IDMC.

The IDMC will review 7-day post-dose 1 safety data of the first 12 Cohort 1 subjects and will convene as needed on an ad hoc basis to ensure the continuing safety of the subjects enrolled in this study. The IDMC will also convene to discuss any situation that meets a study vaccination pausing rule. The IDMC will monitor severe RSV-LRTI as detailed in the IDMC charter. A separate SAP for the IDMC analysis will be provided.

## **4. SUBJECT INFORMATION**

Subject information will be shown for the full analysis set.

### **4.1. Demographics and Baseline Characteristics**

Demographic characteristics and screening/baseline characteristics will be tabulated and summarized with descriptive statistics per vaccine regimen and over all subjects.

The following demographic and baseline characteristics will be summarized.

- Sex (Female/Male)
- Age (years)
- Race
- Ethnicity
- Height (cm), only for Cohort 0
- Weight (kg), only for Cohort 0
- BMI (kg/m^2), only for Cohort 0
- Growth Percentile, weight by age\*, only for Cohort 1
- Growth Percentile, height/length by age \*, only for Cohort 1

### **4.2. Disposition Information**

The number and percentage of subjects screened, subjects in the FA set, subjects in the PPI set, subjects vaccinated and not randomized, subjects randomized and not vaccinated and discontinued subjects (study discontinuation and vaccination discontinuation) with the reason of discontinuation will be tabulated per vaccine group and overall.

Also, the number of subjects and percentage per phase will be tabulated.

### **4.3. Treatment Compliance**

The number of missed vaccinations will be tabulated.

### **4.4. Protocol Deviations**

Major protocol deviations will be summarized.

### **4.5. Concomitant Medications**

The analysis of concomitant therapies will be done using the WHO drug coded terms.

There will be special attention to analgesics/antipyretics such as acetaminophen, non-steroidal anti-inflammatory drugs (NSAIDs) and aspirin, administered during 8 days following each vaccination (00:00 of day of vaccination + 7 days).

Based on their start and stop date, concomitant therapies will be reported in each applicable phase. If a concomitant therapy record misses components of its start and/or stop dates (day and/or month and/or year):

- In case of partial start or stop dates, the concomitant therapy records will be allocated to periods using the available partial information, without imputations. If, for example, only month and year are available, these will be compared to the month and the year of the periods, and the concomitant therapy record will be allocated to the period(s) where these date parts match. This rule may lead to assignment to multiple periods.
- In case of a completely missing start date, the concomitant therapy will be considered as having started before the trial.
- In case of a completely missing end date, the concomitant therapy will be considered as ongoing at the end of the trial.

## 5. SAFETY

Safety analyses will be performed on the FA. Continuous variables will be summarized using the following statistics, as appropriate: number of observations, median, quartiles (Q1 and Q3), minimum and maximum. Frequencies and percentages (one decimal place) will be generated for categorical variables. No formal comparisons between groups will be provided.

Two types of safety tables will be shown. In the by regimen layout, safety data will be analyzed by vaccine regimens as designed per protocol; data will be presented by period as well as over the entire regimen. Denominator for the percentages is the number of subjects in the considered population and period for a certain regimen (incidence per 100 subjects/period). In the second, by vaccine, safety data will be presented by the different vaccines used in the study but by considering every vaccination administered as a separate safety episode. Denominator for the percentages is the number of vaccinations administered of a certain vaccine (rate per 100 vaccinations of a particular vaccine).

### 5.1. Adverse Events (AE)

#### 5.1.1. Definitions

Solicited AEs shown in the tables are extracted from the diary pages of the CRF. For unsolicited AEs, only the AEs starting (grade and/or relation) within the 28-day period following each vaccination will be presented in the safety tables except for SAE, which will be captured and tabulated in the outputs covering the whole study period. All other collected unsolicited adverse events will be presented through listings.

Solicited local AEs will be by definition considered as related to the study vaccine.

The severity of the AEs will be classified as grade 1 to 4. Solicited events that are graded less than grade 1, are not considered as AE. In case no grades are available, the grading of the solicited events will occur according to the grading list in [Attachment 1](#).

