**Figure 1: Enrollment and First Dose Strategy**

\*Two Cohort 0 sentinel subjects, and the parent/legal guardian of 2 sentinel subjects from Cohort 1 will be contacted on Day 3 by telephone to collect safety information.

After each vaccination, all subjects will be closely observed for a minimum of 30 minutes post-vaccination, or a minimum of 60 minutes post-vaccination according to local approvals, to monitor for the development of any acute reactions, or longer if deemed necessary by the investigator. Any unsolicited, solicited local or systemic AEs and vital signs will be documented by study-site personnel following this observation period. Subjectsa will be given a thermometer, ruler and daily assessment (subject) diary with instructions for the proper recording of events. Each subject will record solicited local (at injection site) and systemic AEs and body temperatures, beginning on the evening of each study vaccine dosing day and on a daily basis for the following 7 days. Temperaturesb should be taken at approximately the same time each day, preferably in the eveningc and, for pediatric subjects, additionally whenever the child feels warm. Study-site personnel will collect and review subject diary information and confirm the entries at subsequent site visits.

Unsolicited AEs will be collected from the time of informed consent through 28 days after each dose. For both cohorts, all SAEs will be collected from ICF signature to the end of the study. All AEs, including any that are ongoing at 28 days after each dose, will be followed until clinical resolution or stabilization. Concomitant medications will be collected from the time of each vaccination through 28 days after each vaccination, and additionally outside of these periods when associated with any SAE.

Blood will be collected for immunogenicity assessments as follows:

- Cohort 0: pre-vaccination for first and second doses, and at 28 days and 6 months after the second dose
- Cohort 1: pre-vaccination for first and second doses, and at 28 days and 6 months after the second dose

For Cohort 1, a blood sample will be taken for RSV serology at screeningd; the baseline sample for immunogenicity may either be drawn at the same screening visit or pre-dose on Day 1, at the discretion of the investigator.

Unscheduled study visits may be performed based on investigator's clinical judgment and may include further evaluations, as needed.

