### **5.1.3. Phase allocation of Unsolicited Adverse Events**

Solicited events are always allocated to the respective Post Dose period.

Solicited AEs from the diary will be added to the ADAM database for unsolicited AEs according to the same principles. This means the same event occurring on different days will be allocated to one row with the start date of the AE being the first date of the event and the end date for the event is the last subsequent day of the event. A change in grade will trigger a new row to be added. The same occurs in case of non-subsequent events (for example grade 1 nausea on day 1, 2 and 3 and also on day 6 and 7, which will be allocated to two rows; the duration of the event is 7 days). For further details related to transforming the on-site assessments and diaries of solicited AEs into analysis format please refer to [Attachment 2](#).

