**Attachment 3: Transforming the on-site assessments and diaries of solicited AEs into analysis format**

When creating the analysis dataset for solicited AEs, solicited AEs (recorded by day on the SR and FA domains) need to be converted into the same format as unsolicited AEs (recorded by event). For this purpose, the start date of the AE will be considered as the date of first occurrence of the solicited AE. If on subsequent day(s), the same grade is reported, the last reported date is used as the end date of the AE. A new record is created in case the grade of the event changes. If there is a time gap of at least one day between two (or more) occurrences of the same solicited AE, then the second (and/or next) occurrence will be considered as a new AE. In case no data is reported for a day, this is analyzed as no event reported. If the on-site assessment differs in grade or relatedness with the Day 1 diary data, the on-site assessment should be recorded as a separate record in the database.

The example below shows how the solicited AE should be converted into a format of unsolicited AEs:

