**Data from the Subject Diary**

Subject: 0001

Solicited systemic AE: Headache

	On site assessment	DIARY DATA							
Solicited AE	Day 1 01Jan16	Day 1 01Jan16	Day 2 02Jan16	Day 3 03Jan16	Day 4 04Jan16	Day 5 05Jan16	Day 6 06Jan16	Day 7 07Jan16	Day 8 08Jan16
Grade	2	1	1	0	3	3	1	0	0
Relatedness	Doubtful	Probable							

The data should be converted and stored in the AE dataset as follows:

Subject No.	AE	Start Date (Char)	Stop Date (Char)	Severity	Relatedness	AEID
0001	Headache	01Jan16	01Jan16	2	Doubtful	1
0001	Headache	01Jan16	02Jan16	1	Probable	1
0001	Headache	04Jan16	05Jan16	3	Probable	1
0001	Headache	06Jan16	06Jan16	1	Probable	1

If a solicited AE ends after day 8:

- The last day that AE was reported and the maximum severity (or/and diameter for local AEs) after Day 8 are captured in the CRF. For this a separate record needs to be created, in case this severity deviates from the previous record.

For the **calculation of duration**, the first and last day is used, irrespective of whether interruptions occurred in between by missing reporting days or Grade 0 events. In the above

example, the 4 records contribute to the same AE, therefore AEID (AE identification) is set to the same value and the duration of the AE is set to 6 for all records.

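### SAP 5.1.1 names the diary pages as the source of the solicited AE tables, while Attachment 3 also keeps differing on-site assessments; the conflict leaves it open whether on-site reactions reach the primary safety tables

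*SAP*

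**What the plan says.** **Collection.** Under Protocol 9.1.3.2.1, 9.1.4.2.1 and 9.2.3, site staff assess solicited local and systemic events on site after an observation period of at least 30 minutes, or at least 60 where local approval requires it. Diary recording starts later, "beginning on the evening of each study vaccine dosing day and on a daily basis for the following 7 days" (Protocol 3.1). The primary endpoint in Protocol 2.1.2 covers solicited AEs for 7 days after each vaccination and is not limited to diary data.

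**Tabulation.** SAP 5.1.1: "Solicited AEs shown in the tables are extracted from the diary pages of the CRF". SAP 5.1.3 also names the diary: "Solicited AEs from the diary will be added to the ADAM database for unsolicited AEs according to the same principles".

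**Derivation.** The same section then gives a pointer: "For further details related to transforming the on-site assessments and diaries of solicited AEs into analysis format please refer to". The place it names is the second attachment, which holds the Cohort 1 toxicity tables; the conversion rules are in Attachment 3. Attachment 3 applies "When creating the analysis dataset for solicited AEs". Its condition for using the site finding reads: "If the on-site assessment differs in grade or relatedness with the Day 1 diary data". Where that condition is met, the instruction is that "the on-site assessment should be recorded as a separate record in the database". Its worked example stores an on-site Grade 2 headache beside a Day 1 diary Grade 1 and says that "the 4 records contribute to the same AE".

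**The concern.** The on-site check exists to catch immediate reactions, and the diary opens only that evening. A programmer could obey both texts by storing the on-site row as Attachment 3 requires and then tabulating only diary rows as 5.1.1 says. Incidence and worst grade for a primary endpoint would then depend on which paragraph was followed.

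An on-site reaction left out in this way would have no obvious other place. Protocol Section 12 defines unsolicited AEs as those the diary does not ask about, so an on-site headache does not become unsolicited. SAP 5.1.4 counts subjects without a reported event as event-free. The wrong attachment number in 5.1.3 makes the rule that keeps on-site rows harder to find.

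**Working it through.** **1. Reproduce the SAP's example.** Inputs from Attachment 3: on-site grade 2 on Day 1; diary grades for Days 1 to 8 of 1, 1, 0, 3, 3, 1, 0, 0. Rules: a new row at each change of grade or gap, a separate row for an on-site grade that does not match the Day 1 diary, and duration = last day − first day + 1.

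- Rows: on-site Grade 2 (Day 1); Grade 1 (Days 1–2); Grade 3 (Days 4–5); Grade 1 (Day 6). That is 4 records.
- Duration = 6 − 1 + 1 = 6 days.

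Both match the SAP.

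**2. Compare the two readings.** The last two rows are hypothetical patterns.

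| Pattern | Attachment 3 | Diary rows only |
|---|---|---|
| SAP example | 4 rows, worst grade 3, 6 days | 3 rows, worst grade 3, 6 days |
| On-site 2, diary all 0 | 1 row, worst grade 2 | no event |
| On-site 2, diary 1 on Day 1, then 0 | 2 rows, worst grade 2 | 1 row, worst grade 1 |

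The readings differ when the reaction has gone by evening, or when the on-site grade is the subject's highest. In the SAP's own example the worst grade and duration are the same either way.

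**3. Size per affected subject.** The by-regimen denominator (SAP Section 5) is subjects in the period. Group sizes come from Protocol Table 5; SAP Table 1 still prints 32 and 16 toddlers although SAP 1.2 gives 36 in total. For one subject whose only occurrence of the event was on site:

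- Active toddlers: 1/24 = 4.2 points
- Placebo toddlers: 1/12 = 8.3 points
- Active adults: 1/8 = 12.5 points
- Placebo adults: 1/4 = 25 points

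SAP Section 5 also plans a by-vaccine layout with vaccinations as denominator. If both doses are given to everyone, one such episode is 1/(2 × 24) = 1/48 = 2.1 points in active toddlers and 1/(2 × 8) = 1/16 = 6.3 points in active adults.

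**4. Time to onset.** SAP 5.1.2 defines it as date of first onset − period start date + 1, in days. The on-site check and the evening diary both fall on Day 1, so a reaction still present that evening has onset 1 − 1 + 1 = 1 under either reading. If it had gone by evening and returned on Day 4, say, diary-only onset would be 4 − 1 + 1 = 4 in place of 1. If it never returned, the subject has no onset to count. Omission can therefore leave time to onset unchanged or make it later; it cannot shorten it.

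**The case against.** The strongest reply is that Attachment 3 already settles the matter. It covers both patterns of concern, since gone by evening and milder by evening are each a mismatch of grade. It governs the solicited AE analysis dataset, and 5.1.3 refers the reader to the conversion of on-site data as well as diaries. Keeping an on-site row would have little purpose if no table used it. Further, 5.1.1 does not say that the diary is the *only* source, although its next sentence uses that word for unsolicited AEs. CRF page names are also loose: Protocol 12.3.1 has diary information transcribed into on-site assessment forms. SAP 5.3 tabulates on-site as well as diary temperatures. The table specifications are in a separate document that is not available here.

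Much of this stands. A reader might infer from 5.1.1 that immediate reactions do drop out of the primary endpoint. The documents do not support that, because Attachment 3 retains them and nothing in the SAP gives 5.1.1 precedence over it. Nor do they support a claim that the active arm would lose most: they give no rate of such reactions by arm, and do not say whether the evening entry covers the whole day.

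What the reply does not remove is the conflict. Two statements name the diary as source. No sentence says that on-site records enter the solicited AE tables. The explicit provision for on-site temperature has no counterpart for the other solicited events.

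**Conclusion.** The point holds as an internal inconsistency on a primary endpoint. SAP 5.1.1 and the first part of 5.1.3 conflict with Attachment 3 on whether on-site solicited records count. Loss or under-grading follows only if 5.1.1 is applied as a diary-only filter, and even then only for subjects whose sole or highest-graded occurrence of an event was on site. The per-subject figures of 4.2 and 12.5 points illustrate this for fully enrolled active groups, with all subjects in the period. They are not estimates of bias, since the number of affected subjects is unknown and may be zero. In groups this small, one subject is enough to be visible in a table, so the rule should be fixed before the tables are programmed.

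**What to change.** Make three wording changes in the SAP:

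1. In 5.1.1, state that tabulated solicited AEs are drawn from both the diary pages and the on-site assessment pages, combined under Attachment 3, with worst grade taken over both.
2. In 5.1.3, extend the sentence that names the diary so that it also names the on-site assessment.
3. In 5.1.3, change the reference for the conversion rules from Attachment 2 to Attachment 3.

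The table specifications should be checked against the new wording. The cost is SAP text only: the on-site data are already collected, and Attachment 3 already derives the records.

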### ***Systemic Adverse Events***

Subjects will be instructed on how to record daily temperaturea using a thermometer provided for home use. Subjects should record the temperature in the diary in the evening of the day of vaccination, and then daily for the next 7 days approximately at the same time each dayb. If more than one measurement is made on any given day, the highest temperature of that day will be used in the eCRF.

Fever is defined as endogenous elevation of body temperature  $\geq 38^{\circ}$  C, as recorded in at least one measurement.

---

a Recommended orally for adult subjects; rectally or axillary for pediatric subjects (actual routes to be recorded in the eCRF).

b All Day 8 post-vaccination diary assessments, including temperature measurements, may be collected earlier to coincide with the corresponding clinic visit.

Subjects will also be instructed on how to note daily in the diary for 7 days post-vaccination symptoms of the following events: *for adult subjects* – fatigue, headache, myalgia, arthralgia, chills, nausea and fever (ie, body temperature  $\geq 38$  °C); *for pediatric subjects* – loss of appetite, vomiting, diarrhea, decreased activity/lethargy, irritability/crying and fever (ie, body temperature  $\geq 38$  °C).

The severity of these solicited systemic AEs will be graded by the investigator according to the criteria presented in Section 12.1.3, Severity Criteria.

If a solicited local or systemic AE is not resolved by 7 days post-vaccination, the follow-up will be captured on the diary. The subject will be instructed to record the date of last symptoms and maximum severity in the diary after resolution.

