### 12.1.3. Severity Criteria

All AEs and laboratory data reported as AEs will be coded for severity using the toxicity grading table in [Attachment 1](#) (for Cohort 0), and in [Attachment 2](#) (for Cohort 1). *Note:* For Cohort 0, laboratory values within local laboratory normal ranges (even if within a toxicity grade range), or laboratory values outside normal ranges that are not clinically significant in the judgment of the investigator, should not be recorded as AEs. For AEs not identified in the grading table, the following guidelines will be applied:

**Mild (Grade 1):** Awareness of symptoms that are easily tolerated, causing minimal discomfort and not interfering with everyday activities.

**Moderate (Grade 2):** Sufficient discomfort is present to cause interference with normal activity.

**Severe (Grade 3):** Extreme distress, causing significant impairment of functioning or incapacitation. Prevents normal everyday activities.

**Potentially life-threatening (Grade 4):** Symptoms causing inability to perform basic self-care functions OR medical or operative intervention indicated to prevent permanent impairment, persistent disability.

The investigator should use clinical judgment in assessing the severity of events not directly experienced by the subject (eg, laboratory abnormalities).

For Cohort 0, the toxicity grading scale used for laboratory assessments is based on the FDA toxicity grading table, consistent with the assessment grading used throughout the protocol. If a laboratory value falls within the grading as specified in the FDA table, but also within the laboratory normal limits, the value is considered as normal. For hemoglobin, both the actual value and the change from reference will be graded.

The severity of solicited AEs will be graded in the diary by the subject based on the severity assessment provided in the diary and then verified by the investigator using the respective toxicity grading table.

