### **5.1.2. Analysis of Adverse Events**

Number and percentage of subjects with at least one particular AE (unsolicited/solicited) will be tabulated. Unsolicited AEs will be summarized by System Organ Class and Preferred Term. Solicited AEs will be summarized by class (local, systemic) and preferred term.

For solicited AEs following tables will be provided: summary, by worst severity grade, grade 3, related (systemic only), time to onset (in days) and duration (in days) for most frequent events and body temperature. Note: Duration for solicited AEs is defined as number of days from the start of the event until resolution of the event. The time to first onset is defined as (date of first onset – reference date + 1). The reference date is the start date of the period.

For unsolicited AEs following tables will be provided: summary table (including SAE, fatal outcome, AESI and discontinuation), all events, most frequent, grade 3, permanent stop of vaccine, related, SAE.

Listings and/or subject narratives will be provided as appropriate, for those subjects who die, discontinue study vaccinations due to an AE, or experience a severe or serious AE.

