PT – increase by factor (prothrombin time)	1.0 – 1.10 x ULN**	1.11 – 1.20 x ULN	1.21 – 1.25 x ULN	> 1.25 ULN
PTT – increase by factor (partial thromboplastin time)	1.0 – 1.2 x ULN	1.21 – 1.4 x ULN	1.41 – 1.5 x ULN	> 1.5 x ULN
Fibrinogen increase - mg/dL	400 – 500	501 – 600	> 600	--
Fibrinogen decrease - mg/dL	150 – 200	125 – 149	100 – 124	< 100 or associated with gross bleeding or disseminated intravascular coagulation (DIC)
International Normalized Ratio (INR)***	1.1 to < 1.5 x ULN	1.5 to < 2.0 x ULN	2.0 to < 3.0 x ULN	≥ 3.0 x ULN

\* The laboratory values provided in the tables serve as guidelines and are dependent upon institutional normal parameters. Institutional normal reference ranges should be provided to demonstrate that they are appropriate.

\*\* "ULN" is the upper limit of the normal range.

\*\*\*: For INR, the values in the table are based on the Division of AIDS Table for Grading the Severity of Adult and Pediatric Adverse Events, 2014 (version 2.0)

Urine *	Mild (Grade 1)	Moderate (Grade 2)	Severe (Grade 3)	Potentially Life Threatening (Grade 4)
Protein	Trace	1+	2+	Hospitalization or dialysis
Glucose	Trace	1+	2+	Hospitalization for hyperglycemia
Blood (microscopic) - red blood cells per high power field (rbc/hpf)	1 - 10	11 - 50	> 50 and/or gross blood	Hospitalization or packed red blood cells (PRBC) transfusion

\* The laboratory values provided in the tables serve as guidelines and are dependent upon institutional normal parameters. Institutional normal reference ranges should be provided to demonstrate that they are appropriate.

Vital Signs *	Mild (Grade 1)	Moderate (Grade 2)	Severe (Grade 3)	Potentially Life Threatening (Grade 4)
Fever (°C) ** (°F) *	38.0 – 38.4 100.4 – 101.1	38.5 – 38.9 101.2 – 102.0	39.0 – 40 102.1 – 104	> 40 > 104
Tachycardia - beats per minute	101 – 115	116 – 130	> 130	ER visit or hospitalization for arrhythmia
Bradycardia - beats per minute***	50 – 54	45 – 49	< 45	ER visit or hospitalization for arrhythmia
Hypertension (systolic) - mm Hg	141 – 150	151 – 155	> 155	ER visit or hospitalization for malignant hypertension
Hypertension (diastolic) - mm Hg	91 – 95	96 – 100	> 100	ER visit or hospitalization for malignant hypertension
Hypotension (systolic) – mm Hg	85 – 89	80 – 84	< 80	ER visit or hospitalization for hypotensive shock
Respiratory Rate – breaths per minute	17 – 20	21 – 25	> 25	Intubation

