**Attachment 2: Toxicity tables for cohort 1**

Grading scale used for clinical AEs is adapted from the Division of Microbiology and Infectious Diseases (DMID) “Pediatric Toxicity Tables for Children Greater Than 3 Months of Age (2007)”. For AEs not included in the tables below, severity criteria guidelines will be provided in the full protocol.

Gastrointestinal	Grade 1	Grade 2	Grade 3	Grade 4
Nausea/vomiting	Minimal symptoms; caused minimal or no interference with, school or self-care activities. Child vomits once per day (24h).	Notable symptoms; required modification in activity or use of medications; did not result in cancellation of social activities. Child vomits 2-3 times per day (24h).	Incapacitating symptoms; required bed rest and/or resulted in cancellation of social activities. Child vomits 4-6 times per day (24h).	Unable to ingest food or fluid for more than 24 hours/ $\geq 7$ episodes of vomiting per day or intractable vomiting. Emergency room visit or hospitalization and significant medical intervention/therapy required.
Diarrhea	Consistency of stools changes OR increase of 1-3 stools compared to normal frequency over a 24 hour period.	Liquid stools OR increase of 4-6 stools compared to normal frequency over a 24 hour period.	Increase of $\geq 7$ stools compared to normal frequency over a 24 hour period OR child might need an infusion with fluid without hospitalization.	Emergency room visit or hospitalization and significant medical intervention/therapy required.
Appetite	Some loss of appetite but no decrease in oral intake.	Loss of appetite associated with decreased oral intake.	Almost no appetite, does not eat and/or weight loss.	Emergency room visit or hospitalization and significant medical intervention/therapy required.

Reactogenicity	Grade 1	Grade 2	Grade 3	Grade 4
Systemic reactions				
Irritable/Fussy/Crying/ Screaming	Easily consoled and returns to play easily. He/she has periods of crying fewer than 60 minutes.	Not easily consoled and is not easily interested in playing. He/she has periods of crying lasting between 60-120 minutes.	Very irritable, cannot be consoled and does not play. He/she has periods of continuous crying lasting more than 2 hours.	Inconsolable. Emergency room visit or hospitalization and significant medical intervention/therapy required.

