Lethargy	Minimal symptoms; caused minimal or no interference with school or activities.	Notable symptoms; required modification in activity or use of medications; did not result in loss school or cancellation of social activities.	Incapacitating symptoms; required bed rest and/or resulted in loss of school or cancellation of social activities.	Emergency room visit or hospitalization and significant medical intervention/therapy required.

Other	Grade 1	Grade 2	Grade 3	Grade 4
Fever	38.0-38.4 °C or 100.4-101.1 °F.	38.5-40 °C or 101.2-104.0 °F.	Greater than 40 °C or 104.0 °F.	Sustained Fever: equal or greater than 40C (104.0F) for longer than 5 days.

Reactogenicity	Grade 1	Grade 2	Grade 3	Grade 4
Local reactions				
Pain/tenderness at injection site	Mild discomfort when the injection site is touched; child does not limit use of his/her arm or leg where the injection was done.	Notable discomfort when the injection site is touched; child limits use of his/her arm or leg where the injection was done.	Severe discomfort when the injection site is touched; child avoids use of his/her arm or leg where the injection was done.	Emergency room visit or hospitalization and significant medical intervention/therapy required.
Erythema/redness	≥10 and <25 mm diameter.	≥25 and <50 mm diameter.	≥50mm diameter.	Emergency room visit or hospitalization; necrosis or exfoliative dermatitis.
Induration/swelling	≥10 and <25 mm diameter.	≥25 and <50 mm diameter.	≥50mm diameter.	Emergency room visit or hospitalization; necrosis or exfoliative dermatitis.

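### SAP 5.1.1 grades toddlers' ungraded solicited events on the adult FDA scale, which puts a non-sustained fever of 39.0 °C or more one grade too high

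*SAP*

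**What the plan says.** SAP 5.1.1 covers solicited events with no recorded severity: "In case no grades are available, the grading of the solicited events will occur according to the grading list in" Attachment 1. SAP Attachment 1 is the FDA scale for healthy adult and adolescent volunteers. The sentence makes no distinction between cohorts.

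Protocol 12.1.3 does make one. Its general rule reads "All AEs and laboratory data reported as AEs will be coded for severity using the toxicity grading table in" and then names the table by cohort: adults are graded by Attachment 1, toddlers by Attachment 2. The same section explains where solicited grades normally come from: they are entered in the diary and then "verified by the investigator using the respective toxicity grading table". Protocol 9.2.3, under Systemic Adverse Events, agrees: "The severity of these solicited systemic AEs will be graded by the investigator according to the criteria presented in Section 12.1.3, Severity Criteria".

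The SAP also carries "Attachment 2: Toxicity tables for cohort 1". It has rows for all nine pediatric solicited events listed in SAP 5.1.5 and 5.1.6, and its fever row is the same as the one in protocol Attachment 2. No grading rule in the SAP refers to it.

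The grades feed the outputs named in SAP 5.1.2: "For solicited AEs following tables will be provided: summary, by worst severity grade, grade 3, related (systemic only"), followed by onset, duration and temperature tables. Separately, the part of SAP 5.3 that applies to both cohorts promises a listing of subjects with fever by the FDA table.

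**The concern.** Solicited adverse events are a primary endpoint, and their severity is reported by worst grade and in a Grade 3 table. Followed literally, the SAP would grade an ungraded toddler event on an adult scale. The result would then sit in the same table as investigator-verified grades based on the Cohort 1 scale. The protocol does not allow this, and SAP 1.6, which lists changes to the planned analyses, does not declare it. It deals only with interim analyses and with what the IDMC receives.

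Fever is where a wrong grade can appear, because both attachments grade it and the cut-points differ. In the SAP text available, Attachment 1 contains only serum, hematology, urine and vital-sign tables. For the other eight pediatric solicited events (three local reactions, appetite, vomiting, diarrhea, lethargy, irritability) the fallback as written therefore gives no grade at all.

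**Working it through.** **Inputs.** Adult fever row: SAP Attachment 1 (Grade 3 is "39.0 – 40 102.1 – 104", in °C then °F). Toddler fever row: SAP Attachment 2 (Grade 2 is "38.5-40 °C or 101.2-104.0 °F"; Grade 4 is fever of 40 °C or more lasting longer than 5 days), the same as protocol Attachment 2. Arm sizes: 24 active and 12 placebo toddlers, protocol Table 5. SAP Table 1 still shows 32 and 16, which does not match the 36 toddlers in SAP 1.2, so the protocol's numbers are used. The plan gives no figure of its own to reproduce on this point.

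**Step 1: grade each temperature on both scales.** Each 0.1 °C step was graded, with and without the sustained-fever rule.

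| Temperature (°C) | FDA scale | Cohort 1 scale | FDA minus Cohort 1 |
|---|---|---|---|
| 38.0–38.4 | 1 | 1 | 0 |
| 38.5–38.9 | 2 | 2 | 0 |
| 39.0–40.0, not sustained | 3 | 2 | +1 |
| above 40, not sustained | 4 | 3 | +1 |
| exactly 40.0, longer than 5 days | 3 | 4 | −1 |
| above 40, longer than 5 days | 4 | 4 | 0 |

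Both scales start at 38.0 °C, so the same children count as having fever.

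**Step 2: effect on the severity tables.** The SAP does not say whether its Grade 3 table means exactly 3 or 3 and above, so both readings are shown for a child whose worst fever has no recorded grade.

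| Case | Change in count, Grade ≥3 | Change in count, exactly Grade 3 |
|---|---|---|
| 39.0–40.0, not sustained (2 → 3) | +1 | +1 |
| above 40, not sustained (3 → 4) | 0 | −1 |
| exactly 40.0, sustained (4 → 3) | 0 | +1 |
| above 40, sustained (4 → 4) | 0 | 0 |

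**Step 3: size.** Shift in the Grade 3 or higher percentage = k / n, where k is the number of children of the first kind in one arm. The documents do not give k; the range 0 to 3 is an assumption.

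| k | Active, k/24 | Placebo, k/12 |
|---|---|---|
| 0 | 0 | 0 |
| 1 | 4.2 points | 8.3 points |
| 2 | 8.3 points | 16.7 points |
| 3 | 12.5 points | 25.0 points |

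These are for the by-regimen layout of SAP section 5. The by-vaccine layout counts vaccinations. If every toddler receives both doses and Cohort 1 is shown alone, the denominators are 24 × 2 = 48 and 12 × 2 = 24, so one event is 1/48 = 2.1 points or 1/24 = 4.2 points.

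**The case against.** The best defense is that this is a stale pointer and nobody intended to grade toddlers as adults. SAP 5.1.3 sends the reader to Attachment 2 for the diary conversion, which is actually Attachment 3, so the attachment numbering in that section is out of date. A toddler table cut down to exactly the nine solicited events has no evident use other than grading them. That explanation is plausible, but a programmer who follows 5.1.1 still never reaches the toddler table.

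The rule is also only a fallback. Diary grades verified by the investigator are the main route, and the number of ungraded toddler fevers may be zero, in which case nothing changes. The range of 0 to 3 children shows the size of each step and says nothing about likelihood. The rule is the same in both arms, and no formal comparison is planned. The pausing rules are monitored by the principal investigators and the study responsible physician, so they do not depend on this derivation. All of this stands. It limits how often the error would show but leaves the rule in conflict with the protocol.

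Two further points stand in part. SAP 5.3 conflicts with the protocol only if the fever listing displays grades; if the FDA table merely selects subjects at 38.0 °C or above, both scales select the same children. And SAP Attachment 1 as printed has no local or general systemic rows for adults, unlike protocol Attachment 1. Correcting the reference for toddlers does not fill that Cohort 0 gap, which is a separate matter.

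**Conclusion.** The concern holds. SAP 5.1.1 states a rule that contradicts protocol 12.1.3 for Cohort 1 and can put a wrong grade into a primary-endpoint severity table. An ungraded, non-sustained toddler fever of 39.0 °C or more is graded one too high. The exceptions are confined to sustained fever: one grade too low at exactly 40.0 °C, and no difference above it. Each child moved from Grade 2 to 3 adds 4.2 points (active) or 8.3 points (placebo) to the Grade 3 or higher rate, given 24 and 12 toddlers and the by-regimen layout. The total effect depends on how many toddler fevers lack a grade, which the documents do not give. Fever occurrence and the temperature-interval tables are unaffected. It should be corrected because the contradiction is clear and the correction costs very little, even though it may turn out to affect no child.

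**What to change.** In SAP 5.1.1, state that solicited events without a recorded grade are graded by Attachment 1 for Cohort 0 and by Attachment 2 for Cohort 1. This also supplies grades for the eight other pediatric events. In SAP 5.3, make any grade shown in the fever listing cohort-specific in the same way, or state that the table is used only to select subjects. For Cohort 1, both passages then agree with protocol 12.1.3.

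The cost is two wording corrections and a grading lookup keyed on cohort. No new data are needed. In the same edit, the SAP 5.1.3 reference for the diary conversion can be corrected to Attachment 3, and the authors can check whether SAP Attachment 1 should carry the adult local and systemic rows found in protocol Attachment 1.
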